Study Participants	Staff and service-users		
Planned Study Period	Sept 2021-May 2023		
Research Aim / Question(s) / Objective(s)	To generate policy and service recommendations for CJ substance abuse services through a robust, mixed-methods evaluation of an innovative pilot Research questions: How is a public health pathway for alcohol and substance users in the criminal justice setting developed and implemented? And:		
	Does it achieve: co-ordination between services, acceptability, engagement and short-term outcomes?		
	Research objectives: To explore the context and the process of development and implementation of the pilot To evaluate the experience, acceptability and perceived impact of service providers in delivery To evaluate the experience and acceptability among service-users in each tier and across population groups		

FUNDING AND SUPPORT IN KIND

FUNDER(S) (Names and contact details of ALL organisations providing funding and/or support in kind for this study)	FINANCIAL AND NON FINANCIAL SUPPORT GIVEN
NIHR	This study forms part of a grant of £2.5million

ROLE OF STUDY SPONSOR AND FUNDER

PHIRST South Bank is one of 6 UK Public Health Intervention Responsive Studies Centres funded by NIHR. It is hosted by London South Bank University.

ROLES AND RESPONSIBILITIES OF STUDY MANAGEMENT COMMITEES/GROUPS & INDIVIDUALS

PHIRST South Bank Centre Executive Committee (CEC)

The CEC sits within the sponsor organisation, LSBU. It has management and governance responsibility for PHIRST South Bank and is made up of the Centre Co-Investigators, senior academic staff at LSBU and a lay representative from LSBU's People's Academy

PHIRST South Bank Advisory Group

The Advisory Group provides overall supervision for the project on behalf of the Project Sponsor and Project Funder and ensures that the project is conducted to the rigorous standards set out in the Department of Health's Research Governance Framework for Health and Social Care and the Guidelines for Good Clinical Practice. Membership has been approved by NIHR.

Project Stakeholder Group

A local stakeholder group is in place to ensure liaison between the research team, the local project leads and PPIE representatives. The group is represented by Greater Manchester Combined Authority and representatives of the projects included within the Communities Against Gambling Harm programme.

KEY WORDS:

Criminal justice, substance misuse, alcohol misuse

STUDY PROTOCOL

1. BACKGROUND

Policy context

The policy and service context of Criminal Justice (CJ) services is rapidly evolving. Recent national policy has set out plans for increased funding for substance misuse services and a key policy aim is to increase referrals into treatment in the criminal justice system (HM Government, 2021). Yet, significant variation exists at the local level, following the end of the nationally mandated Drug Intervention Programme (DIP) in 2013 (Sondhi and Eastwood, 2021). CJ services that operate in the custody suite are a mix of DIP and alcohol arrest referral schemes (Sondhi and Eastwood, 2021) while NHS "Liaison and Diversion" (L&D) services have achieved national spread, amidst increasing interest in specifically public health (rather than public safety) strategies (Chariot and Heide, 2018; Marlowe, 2003). While national policy aspires to partnership working and joined-up, service provision (HM Government, 2021), precisely how the various services in operation can be coordinated locally remains to be seen.

Intervention of interest

This project evaluates an alternative and innovative way of working from the DIP model of custody suite engagement. The model consists of a new referral process within the custody suite that will allow for a proactive, targeted and layered approach for addressing the needs of different cohorts in Nottinghamshire. It is more proactive than DIP and involves the coordinated input of a range of stakeholders, such as the police, probation, women's aid and other support providers. The model has been developed by Change Grow Live (CGL), who have delivered Nottinghamshire's integrated substance misuse service since October 2014. The focus of the CGL team is to support people with their offending behaviour and substance misuse needs.

Central to CGL's new model is a layered menu of interventions, with service-users being assigned to one of three Levels after an initial assessment in the custody suite:

- Level 1 universal provision of a wellbeing pack that consists of information that is tailored to the service-users substance abuse behaviours. The pack includes information about alcohol and substance abuse, harm reduction advice and contact details for CGL and other providers. The inclusion of alcohol represents a break from the DIP model, which focused solely on heroin and crack cocaine, and represents rising awareness of the crucial role of alcohol in violent crime.
- Level 2 selective provision of the standard CGL offer, including 1 to 1 counselling sessions, support from volunteers and referral options to a variety of treatment and support services. Level 2 is targeted at repeat offenders and may be entered into on a voluntary or mandatory basis.
- Level 3 assertive outreach to engage the most prolific of offenders (i.e., offenders
 who commit more than three offences within six months). A multi-agency panel
 undertake a mandatory initial assessment for these offenders which is followed by
 assertive outreach support for a time-limited period from a CJ Recovery Coordinator.
 The service will work with up to 18 people at Level 3.

The three levels aim to more effectively address service-user needs and enhance their engagement with the service. The model is underpinned by person-centred philosophy and is proactive in the sense that it aims to identify people earlier in their journey through the CJ system and facilitate intensive support for the most prolific offenders.

[figure not shown]
2. RATIONALE

The CGL Nottinghamshire service presents a unique opportunity to evaluate the early implementation of a new public health and CJ collaboration that consists of a new referral process and service pathway that may more effectively coordinate person centred local services. In a rapidly changing policy and service context in which local services are highly varied and lacking in coordination (Sondhi and Eastwood, 2021), local stakeholders need evidence to guide their efforts if the policy goal of reduced substance use-related crime is to be achieved (HM Government, 2021). This is vitally important as substance use-related crime may be increasing at significant cost to those directly affected and the wider society (Allen and Tunnicliffe, 2021). The evaluation has been specifically designed to generate learning from the Nottinghamshire pilot for CJ services in other areas. The timing of the evaluation also presents an opportunity to consider the local impact of recent national policy; insight about the effectiveness of national policy to facilitate local, service coordination is anticipated

3. THEORETICAL FRAMEWORK

A logic model of the CGL service redesign is represented in Figure 1. This was developed through a series of co-design workshops with local stakeholders, using Theory of Change (ToC) methodology (Breuer et al., 2016). The evaluability assessment carried out during the co-design workshops revealed that the pilot is not yet fully live and processes for implementation are still in development. While CGL stakeholders had a clear ToC for the intervention during the workshops, they recognised that a rapidly changing policy context meant that adaptations to the planned intervention would be required. Discussions were planned with diverse stakeholders, including local authority commissioners and NHS L&D services, about how to improve coordination across services; it was anticipated that the proposed service re-design would change, as a result of these discussions. Furthermore, the implementation strategy for the new referral process had not been planned and it was anticipated that the pathway would have to be adapted on delivery in order to, for example, embed in local systems and routines. An iterative rollout was therefore planned for the custody suite. Hence, a separate, implementation strategy column was incorporated into the logic model to reflect the significance of local stakeholder efforts in facilitating the pilot's implementation (see Figure 1).

Figure 1: Logic model of Nottingham CJ service

The logic model will be developed and refined over the course of this evaluation through a combination of qualitative research and surveys, across three work packages. Senior stakeholders, frontline staff and service-users will participate. Normalisation Process Theory (NPT), which identifies and characterises key mechanisms that promote or inhibit the implementation of complex interventions (May et al., 2018), will provide sensitising concepts for WP1 and WP2, as these focus on the implementation of the pathway and staff and service provider perspectives. NPT highlights the dynamic role of context in implementation processes and provides concepts for characterising mechanisms, barriers and enablers. The use of NPT will enrich interpretations of what is implemented in the pilot and the factors that explain success or failure. Elsewhere, for example, NPT has been used to theorise factors peceived by GPs to affect the implementation of an internet-based cognitive behavioural therapy intervention (Wilhelmsen et al., 2014).

Close attention to implementation and staff views and experiences in WP1 and WP2 will be complemented, in WP3, with an investigation of service-user experience and acceptability. This will be crucial to evaluating the core intervention mechanisms and for assessing, for example, the effectiveness of the levelled, referral approach to coordinate services around service-user needs. The work package will involve a survey to explore service-user readiness to change behaviour at Level 1 which will be framed by the COM-B framework, which has been extensively applied in substance abuse therapy (Gilchrist et al., 2021). The logic model will provide a framework for integrating insights gleaned from across the work packages and will be developed using techniques for modelling complex interventions (Mills et al., 2019; Mills et al., 2022).

4. RESEARCH QUESTION/AIM(S)

4.1 Aim:

• To generate policy and service recommendations for CJ substance abuse services through a robust, mixed-methods evaluation of an innovative service re-design

4.2 Questions:

 How is a public health pathway for alcohol and substance users in the criminal justice setting developed and implemented?

And

• Does it achieve: co-ordination between services, acceptability, engagement and short-term outcomes?

4.3 Objectives

- 1. To explore the context and process of development and implementation of the pilot
- 2. To evaluate the experience, acceptability and perceived impact of service providers in delivery
- 3. To evaluate the experience and acceptability among service-users in each tier and across population groups

4.4 Outcomes

- An empirically informed Theory of Change including logic model and accompanying narrative – of a public health pathway for alcohol and substance users in a criminal justice setting
- Evidence-informed policy and service recommendations for commissioners and service providers aiming to enhance the coordination of criminal justice services around the service-user

5. STUDY DESIGN and METHODS of DATA COLLECTION AND DATA ANALYIS

5.1. Overview of work packages

WP1 will address research objective 1 via reflective diaries, document analysis and interviews with senior stakeholders at commissioning and management level. A final workshop will bring key CGL stakeholders together for a final reflection on the logic model. WP2 and WP3, which respectively address objectives 2 and 3, will initiate once the CJ pathway has been implemented in the custody suite. These work packages will primarily be based on small-scale surveys, qualitative interviews and focus groups to develop insight about the experience and acceptability of the pathway for service providers/staff and service-users; longer-term outcome evaluation is not feasible because of the intervention's early stage of development. Table 1 summarises each of the work packages and maps them to the 3 research objectives.

Table 1: Overview of work packages

WP summary	Data collection method and sample	Rationale	Research objectives
WP1: implementation study	Reflective diaries kept by 2 CGL staff, researcher field notes, document analysis of national policy documents and local service documentation, semi- structured interviews with senior staff stakeholders (n-8 to 12), 1x final workshop	The reflective diaries and researcher field notes will capture details of the process of implementation; analysis of relevant policy and service documentation and the interviews with senior staff will explore crucial macro-level policy and meso-level organisational factors for understanding the pilot context; the interviews and final workshop will enable logic model development	1
WP2: staff acceptability and experience study	Qualitative interviews (n-12 to 24) and small-scale survey (n-12) with staff involved in delivering, referring into or working with service-users along the pathway; summative, end-point interviews with core CGL staff (n- 2 to 4)	Qualitative interviews with service managers and frontline staff will explore the practical implementation and use of the pathway and provide insight into the perceived value and benefit to staff of the various agencies involved; the survey will capture a broad array of views about the pathway among custody suite staff; the summative interviews will tap into the final views and learning of core CGL staff	2
WP3: service- user acceptability and experience study	Survey research, qualitative interviews (n-16 to 24), case study research and the descriptive analysis of service data	Survey research at Level 1 will enable the research team to evaluate service user's experience of the initial assessment in the custody suite and the welcome pack, in terms of it's potential to facilitate behaviour change; survey research at Level 2 will assess experience and acceptability among services while qualitative interviews will assess these in greater depth; case study research of a small number of cases, including observations and interviews, will provide insight into user experiences at Level 3; descriptive analysis of service data will provide insight into referrals and interventions across the levels during the pilot, as well as information on demographics and health needs	3

Work package 1:

Overview

This qualitative work package will address research objective 1: it will investigate the context and process of development and implementation of the pilot. It will develop and refine the ToC set out in Figure 1 ahead of WP2, taking into account adaptations made in light of national policy changes.

Reflective diaries, document analysis and stakeholder interviews

Two core staff with development responsibility (representing Public Health Commissioning and Change, Grow, Live). who are leading the pilot will record observations in reflective diaries as they develop and implement the pilot. They will be provided with a prompt sheet that outlines some key questions that the research team are interested in to ensure that notes are relevant to WP1's aim (see Appendix). CGL staff will be asked to record interactions with key stakeholders and identify candidates for possible interview, based on their perceived relevance to the pilot and emergent questions of interest. Members of the research team will also keep reflective diaries and will capture details of conversations with the core development staff to capture information that may be missed in the CGL staff diaries.

Document analysis of key national policy documents (e.g., HM Government, 2021) will identify key policy objectives for CJ substance misuse services and anticipated mechanisms for achieving them; document analysis of local service documentation will provide insight into historic arrangements and services across Nottinghamshire and how these are changing in response to national policy. Senior stakeholders at commissioning and management level will be sampled for interview via a combination of purposive sampling and snowballing techniques. This will ensure relevance and flexibility in the sample, as WP1 unfolds. Senior staff leads of services central to the scheme or who refer to and/or regularly liaise with the core service will be invited to participate, including senior staff from CGL, the police, the local authority public health department and the NHS. The research team is anticipating that n-8 to 12 interviews will be undertaken, based on initial discussions with CGL staff and some flexibility to allow snowballing to occur. NPT (May et al., 2018) will provide sensitising concepts to guide topic guide development to ensure that key factors that affect the quality of implementation are covered. Interviews will explore how senior CGL staff and wider, senior stakeholders perceive the proposed CJ pathway and barriers and enablers to its implementation. The organisation of CJ services locally will be explored, along with the impact of, and responses to recent national policy. The aim will be to provide a picture of how the local service context is being shaped by national policy and to draw out the implications of this for the pilot.

A final workshop with the CGL staff will refine the logic model set out in Figure 1, with the workshop being recorded and transcribed for later analysis; the 3x initial workshops will also be transcribed for later analysis. The final workshop will also provide a forum to finalise thinking about the sample sizes for WP2 and WP3; WP1 insights will also inform topic guides and survey questions in later work packages.

Work package 2:

Overview

This qualitative work package will address research objective 2: it will investigate the experience, acceptability and perceived impact of the CJ pathway among service providers and staff involved in its delivery and use.

Qualitative interviews and survey research

Qualitative, semi-structured interviews will be carried out with key staff members to ascertain their views of the CJ pathway during the pilot. Given the need to avoid placing excessive research demands on busy service personnel, the research team will engage local stakeholders to organise these at a convenient time. Service managers who have a role managing relevant frontline staff will be purposefully sampled for the interviews, along with the frontline staff themselves. It is not possible to estimate precise sample sizes for these cohorts; the numbers provided here are early estimates, based on initial discussions with CGL staff. WP1 will inform decisions about sample sizes and also the precise staff groups and agencies involved. Topic guides will be framed by NPT to ensure that key factors that affect implementation are covered (May et al., 2018). For example, the interviews will explore the "coherence" of the pathway to service managers, along with other NPT constructs: N-4 to 8 service managers are anticipated for interview. A survey of and interviews with custody staff will explore their views and experience of the pathway, and barriers and enablers to its use: an estimated n-12 participants for the survey and n-2 to 4 participants for the interviews are anticipated. In addition, interviews with key CGL staff (n-2 to 4) and staff of the various agencies (n-4 to 8) who refer into, or deliver interventions as part of the pathway will be carried out. These interviews will explore staff's practical experience of engaging with service-users, from the point of referral in the custody suite through the interventions provided at Levels 1, 2 and 3. Finally, n-2 to 4 summative interviews at the end-point of the pilot, with core CGL and PH Commissioning staff, will ascertain their final views on the effectiveness of the proposed pathway on the various outcomes specified in the logic model (Figure 1).

Work package 3:

Overview

This work package will address research objective 3: it will examine the experience and acceptability of the CJ pathway among service-users in each level of service and across population groups.

Survey research, qualitative interviews, observations and case studies

Data collection methods will differ for each level of service:

• At Level 1, a brief survey will be integrated into the computerised assessment that service-users have, as part of the CJ pathway, on entry into the custody suite. CGL staff will be trained in how to administer the survey, including the taking of informed consent. Survey questions will explore service-user readiness and motivation to change their behaviour in relation to their substance use, and their knowledge about potential sources of support. This will enable the research team to assess whether the information pack is congruent with service-user motivation to change and whether it is proving an effective mechanism for conveying information about services. The COM-B framework, which has been extensively applied in substance

- abuse therapy (Gilchrist et al., 2021), will frame survey questions. The survey will be open for a 3-month window during the pilot.
- At Level 2, a further survey will explore the experience and acceptability of the CJ pathway to service-users while n-4 to 6 semi-structured qualitative interviews will be carried out. This figure is based on initial discussions with CGL stakeholders about what is a feasible number, given likely service-user footfall and engagement, and may change as a result of WP1 learning. The interviews will explore how serviceusers have found the experience of the referral process in the custody suite, subsequent contact with CJ services and any interventions provided. CGL staff and local PPI personnel will assist in the recruitment process in both the survey and qualitative interviews, with the survey being open to all service-users at Level 2 for a 3-month window during the pilot. For the interviews, service-users will be purposely sampled to ensure diversity across key population groups and whether service-user engagement is on a mandatory or voluntary basis. The location and timing of the interviews will be decided by the research team, staff and the service-users on a case-by-case basis. This may help service-users feel at ease and make them more likely to open up about their experiences. The data gleaned from the interviews will provide crucial insight into the impact of the new pathway on service-users and whether it contributes to improved service-user outcomes listed in the logic model (see Figure 1).
- At Level 3, in-depth case studies with n-4 to 6 service-users will explore their experience and acceptability via rapid ethnography (Vindrola and Vindrola-Padros. 2018) and interviews. The figure for the sample size is an estimate at this stage, based on discussions with CGL stakeholders about what is a feasible number, and may change as a result of WP1 learning. Purposive sampling will ensure diversity across key population groups, with CGL staff and local PPI personnel once again assisting in the recruitment process. Researchers will observe key interactions between staff and the service-users along the pathway, including activities such as needs assessments, follow-ups and the delivery of substance-misuse treatments. Researchers will record their observations in field notes. The observations will provide crucial insight into the operation of the pathway on the ground, and how the wider pathway re-design is affecting micro-level interactions and relationships between staff and service-users. X2 interviews with the service-users in the sample will explore, in detail, their experiences of the pathway and the interventions they receive along it, barriers and enablers to their engagement the service and. specifically, their views on the assertive, outreach support component, which is unique to Level 3.

Routine, descriptive data

Routine descriptive information about service-users, referrals and interventions delivered will be obtained to provide insight about service-users and activity over the course of the pilot. This data will be obtained from the National Drug Treatment Monitoring System (NDTMS)-CJIT dataset. Referral and intervention data gleaned from this dataset will provide insight into how the CJ pathway is functioning during the pilot and provide context to the qualitative research. The service-user data and information about substance-misuse problems will also enable the research team to consider how service-user demographics and local health needs shape the pathway's effectiveness. This will be important for considering the potential transferability of the CJ pathway to other areas. This information will also enhance future service planning and the wider public health agenda by identifying if there is under or over representation in service use amongst different groups.

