6. STUDY SETTING

WP1 and WP2 interviews will be carried out remotely over Teams. The study settings for WP3 will reflect where service interventions take place and include CGL and police service areas and locations where the assertive outreach component is delivered. The precise timing and location of the research activities will be sensitive to service-user preferences in an attempt to maximise their engagement. CGL staff and local PPI personnel will assist in the recruitment process.

7.SAMPLE AND RECRUITMENT

WP1

• The 2 CGL staff will be recruited at the start of the research for the reflective diaries via purposive sampling; recruitment of n-8 to 12 senior stakeholders will proceed via purposive sampling and snowballing; CGL stakeholders will be invited to attend the final workshop to refine the logic model, ahead of WP2.

WP2

 Recruitment of staff, including core CGL staff, senior managers and frontline staff, will proceed via purposive sampling and snowballing; n-14 to 28 are anticipated for interview while n-12 are anticipated for the small-scale survey of custody staff. WP2 sample sizes are estimates based on discussions with CGL stakeholders and will be finalised over the course of WP1.

WP3

• All service-users will be made aware of the survey at Level 1, during their initial assessments, via whole population sampling: the survey will be open for a 3-month period. Similarly, all service-users will be made aware of the survey at Level 2, with the survey being open for a 3-month period. Recruitment of service-users into the qualitative research across Levels 2 and 3 will be informed by purposive sampling to ensure a diversity in the sample across key population groups and whether service-user engagement is on a mandatory or voluntary basis: n-16 to 24 interviews are anticipated across Levels 2 and 3, with the Level 3 interviews being conducted as part of n-4 to 6 in-depth case studies. WP3 sample sizes for the qualitative research are estimates based on discussions with CGL stakeholders and will be finalised over the course of WP1.

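### The Level 1 survey sits inside the entry assessment and lists no experience domain, so as described it can give baseline readiness but cannot show what the pack conveys or how Level 1 is experienced

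*Protocol*

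**What the plan says.** **Timing of the survey.** Protocol section 5.1 (Work package 3, Level 1) states that "a brief survey will be integrated into the computerised assessment that service-users have, as part of the CJ pathway, on entry" into custody. Section 7 (Sample and Recruitment, WP3) agrees: "All service-users will be made aware of the survey at Level 1, during their initial assessments, via whole population sampling". The survey is open for 3 months, and no later survey contact is named for Level 1.

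**Timing of the intervention.** Section 1 describes "service-users being assigned to one of three Levels after an initial assessment in the custody suite", and describes Level 1 as "universal provision of a wellbeing pack that consists of information that is tailored to the service-users substance abuse behaviours".

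**Content.** Section 5.1 lists readiness and motivation to change, and knowledge of where support can be found. Section 3 likewise presents it as a survey of readiness to change.

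**Purposes.** Section 5.1 gives two: whether the pack is congruent with motivation, and "whether it is proving an effective mechanism for conveying information about services". The WP3 row of Table 1 adds that the survey will let the team "evaluate service user's experience of the initial assessment in the custody suite and the welcome pack", with regard to the pack's potential to facilitate behaviour change.

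**Objective served.** Objective 3 in section 4.3 is "To evaluate the experience and acceptability among service-users in each tier and across population groups".

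**The concern.** A question about what a pack has conveyed, or how it was received, needs answers from people who have had the pack. The described order of events points the other way: assessment with embedded survey, then Level assignment, then a pack that depends on what the assessment found. The listed content also differs from the content that Table 1 and Objective 3 call for.

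At stake are the claims made from this survey. The study's outputs are a revised logic model and recommendations for commissioners and providers. If entry knowledge is reported as evidence on the pack, those outputs rest on a measure that does not bear on it. No later analysis can recover post-pack answers that were never collected, so this is a matter of data collection and not a detail to be left to an analysis plan.

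**Working it through.** No arithmetic applies: the Protocol gives no sample size, error rate or target figure for this survey, and the point depends on none. The check sets the order of events and the listed content against the stated purposes.

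**Step 1. Where can the survey fall relative to the pack?** The Protocol does not state the moment of handover, so each possibility is taken in turn.

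- *Pack given after the assessment.* This is the natural reading of section 1, since Levels follow the assessment and tailoring needs its answers. All first-contact answers then precede the pack.
- *Pack given during the assessment, with the survey at its end.* The person has had no time to use the pack, and knowledge is still measured only once. With no earlier value and no comparison group, the answer cannot be separated from what the person already knew.
- *Person detained before and given a pack then.* Exposure is possible, but no item or analysis is described that would identify these people. Their answers are pooled with first-contact answers.

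Under none of the three does the survey as described yield an interpretable measure of what the pack conveyed.

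**Step 2. Which stated purposes can the listed content serve?**

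| Purpose | Where stated | Can the survey as described serve it? |
|---|---|---|
| Is the pack congruent with motivation to change? | Section 5.1, Level 1 | Partly: baseline motivation can be set against pack content |
| Does the pack convey information about services? | Section 5.1, Level 1 | No: one knowledge measure, apparently pre-pack, no comparison |
| Experience of the assessment | Table 1, WP3 | No: no experience domain listed, and the assessment is still under way |
| Experience of the pack | Table 1, WP3 | No: no experience domain listed, and the pack is apparently not yet received |
| Acceptability at Level 1 | Objective 3 | No: no acceptability domain listed |

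The Level 2 survey, by contrast, is expressly described in section 5.1 as covering experience and acceptability.

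**Step 3. Does another source cover people who receive only Level 1?**

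- Section 7 places the service-user interviews at Levels 2 and 3, with the Level 3 interviews held within the case studies.
- Level 2 interviews ask about the custody referral process, but section 1 says Level 2 is aimed at repeat offenders.
- Level 3 observation includes needs assessments, again among Level 3 users.
- WP2 staff interviews cover all three Levels, and the diary template asks how service-users are reported to be finding the changes. Both are second-hand accounts.
- The routine dataset describes users, referrals and interventions, not experience.

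These sources give some indirect evidence on the shared custody step. None asks a person whose only contact was Level 1.

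**The case against.** The case for the plan has real substance.

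- **The handover time is inferred.** The pack is offered to everyone, so it need not wait for a Level decision, and tailoring needs only the substance-use answers. Table 1 suggests that the authors meant the survey to follow both assessment and pack. A reader might therefore go too far in inferring that the pack cannot exist when the survey is answered. The documents support only that it apparently has not been given, or has not been used. Step 1 shows that the conclusion does not turn on which of these is true.
- **The questionnaire is not shown and is not final.** Section 5.1 says WP1 will inform the survey questions, section 8.5 gives the PPIE group oversight of the data collection tools, and section 10 schedules their development and piloting. It would be wrong to assert that the survey has no experience items; the Protocol simply lists no such domain. Adding items without moving them would still leave the timing problem.
- **The survey is not without use.** The congruence purpose survives, and Table 1's reference to potential for behaviour change partly fits a readiness measure.
- **Misreading is a risk, not a stated rule.** A reader might infer that low entry knowledge would be scored as the pack failing, and high knowledge as success. Section 5.2 sets no such rule.
- **Other sources touch Level 1.** It is too strong to say that nothing else bears on it. What is missing is direct evidence from people who receive only Level 1.
- **Scale.** These are small surveys in an early formative evaluation, which argues against treating the point as critical.

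All of these limits stand. What remains is a mismatch between section 5.1, Table 1, section 7 and Objective 3 that the Protocol does not resolve.

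**Conclusion.** The point holds in this form and should be fixed; it does not threaten the study as a whole. As described, the Level 1 survey supports statements about baseline readiness, motivation and knowledge, and helps judge congruence of the pack with motivation. It does not support statements about whether the pack conveys information, or about experience of the assessment and pack. Its size is one tier of the three in Objective 3: people who receive only Level 1 have no direct service-user measure of experience or acceptability.

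This rests on two assumptions. The first is that the survey is answered within the entry assessment, as sections 5.1 and 7 both indicate. The second is that the final questionnaire follows the domains listed in section 5.1. If the sponsor already intends a post-pack section with experience items, the Protocol needs only to say so.

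**What to change.** 1. Keep readiness, motivation and knowledge of support at entry, and label them as baseline.
2. After the pack is handed over, at the end of the same custody contact, repeat the knowledge item and add two or three items on experience and acceptability of the assessment and the pack. Placing them there keeps people who receive only Level 1 in the sample.
3. State the moment of handover, so that section 5.1, Table 1 and section 7 describe the same sequence.
4. Treat any items at a later service contact or in the Level 2 survey as descriptive only, because they miss people who receive only Level 1. Treat any comparison by earlier receipt of a pack the same way, because earlier receipt is confounded with repeat detention.
5. If post-pack items are not possible, limit the purposes in section 5.1 and Table 1 to baseline readiness, motivation, knowledge and congruence. State under Objective 3 that service-user experience and acceptability at Level 1 are not directly assessed.

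**Cost.** A few items moved or added to an instrument that is still to be finalised, a slightly longer custody contact, and some loss of completion on the later items. The repeated item would measure immediate knowledge only, not retention or use of services. The fallback costs only rewording, but it gives up part of Objective 3.
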